### **Qualitative Assessment: Phone Interviews**

To assess feasibility and acceptability and potential barriers and facilitators of the SEEK intervention, we will conduct 30-minute semi-structured phone interviews with purposively selected (based on role, practice type, training strategy and presence of behavioral health) subsamples of 5 groups: practice leaders, PCPs, behavioral health professionals, office staff and parents, at 3 time points. For the first 3 groups, these will be around the start of the intervention (probing adoption) and 11 and 21 months later. For the last 2 groups, interviews will be at 11, 20 and 32 months following start of the intervention, after they have experienced SEEK. Interviewers will

use a semi-structured guide similar to one previously employed. Participants will be asked about their experiences with SEEK, assessment of training and implementation support, challenges in delivering the intervention and recommendations for addressing the challenges. Interviews will be conducted by telephone and will be digitally recorded and professionally transcribed for analysis.

## **Measuring Costs**

The cost analysis will provide estimates of the overall practice-level costs associated with implementing SEEK. Cost measurement will be organized using the Cost of Implementing New Strategies (COINS) framework which provides a structure for measuring and categorizing costs. Implementation costs include all resources used to deliver SEEK. COINS maps onto the SIC, by tracking the costs and resources needed to complete each implementation activity. In SEEK II, PCPs in the intervention arm did not require more time per child than did controls. It seems reasonable to apply this to the current study, rather than conduct another time study.

## **Data Analysis Plan**

**General Considerations.** Standard statistical methods for calculating point estimates, confidence intervals, and p-values require the assumption of independence. However, due to participants being clustered within healthcare systems and within practices, this assumption cannot be made. To account for the lack of independence among multiple measures within the same system or practice, we will use random effects (i.e., hierarchical) models. In these models, we will include a random effect for system and for practice. In analyses involving multiple measures from the same person, we will include a random effect for each one. These models can be fitted using SAS Proc GLIMMIX, which fits models for both quantitative and binary outcomes. There will be diverse analyses based on the data. Below we highlight the main analyses for each Aim. The qualitative data (see below) will inform the models through processes of convergence (i.e., triangulation) and expansion (i.e., explanation of unexpected findings from analyses of quantitative data).

Sex as a biological variable will be considered across multiple levels of analyses. At the PCP, parent, and child levels of analyses, there is the potential for variation in implementation outcomes related to sex. Analyses will include a test for sex differences; when differences are noted, additional analyses will examine the influence of additional contextual factors on these outcomes.

**Aim 1. Compare alternative approaches to implementation of SEEK with respect to clinical and implementation outcomes.** To address aim 1a, we will compare practices randomized to MOC to practices randomized to IND with respect to clinical and implementation outcomes. These include perceptions of the training from the PCPs' evaluations, scales from the SEEK PCPQ (e.g., Competence in addressing problems) and the PCP Survey (e.g., Ease of Delivery. We will also compare the groups with respect to rates of screening and parents' receipt of services and satisfaction with the PCP. For quantitative outcomes, statistical inference will be based on linear regression models; for binary outcomes, inference will be based on logistic regression models, accounting for repeated measures within PCP and system. For example, for PCPs reported Competence we will fit this model:  $E(\text{Competence}_{ijkl}) = \beta_0 + s_i + p_j + i_k + \beta_1(\text{POST}) + \beta_2(\text{POST})(\text{MOC-4})$  where Competenceijkl stands for the competence score measured at the lth time point (l=1 or 2 for baseline or follow-up respectively) of the kth PCP in the jth practice of the ith system, and  $s_i$ ,  $p_j$ ,  $i_k$  are random effects for system, practice and PCP respectively; POST=1 if it is a post-training measure and 0 otherwise, MOC = 1 if the PCP was trained using MOC and 0 if IND, and  $\beta$ 's are parameters to be estimated. Note this model assumes that the mean baseline scores are the same in both groups, as recommended for randomized studies. This model can be fitted using restricted maximum likelihood. To avoid possible biases due to selective attrition from the training, the primary analysis will follow the "intention to treat" principle including all those randomized. Secondary analyses will be based on groups defined by training received. To address Aim 1b we will compare practices who choose SEEK-online to practices who choose the traditional approach using the same statistical methods as described for Aim 1a. Outcomes of interest will include staff satisfaction, costs, rates of screening, receipt of services, and parental satisfaction.

**Aim 2. Examine variations in SEEK's implementation process and impacts and understand associated barriers and facilitators in pediatric and family medicine practices.** We will determine the proportion of practices that agree to adopt SEEK. We will then quantitatively assess the relationship between practice characteristics (e.g., demographics, EBP attitudes) and willingness to adopt SEEK. The most important independent predictors will be determined using multivariable logistic regression models. Among those that do adopt SEEK, we will assess their degree of completeness, speed, and quality of implementation using the SIC. Completeness will be summarized using the final stage attained (0-8). Speed will be summarized by the duration in each stage, and quality by the proportion of activities performed at each stage, and overall. The distribution of these variables will be determined, overall and separately, based on the type of

practice. The distribution of time to achieve each phase will be estimated using the Kaplan-Meier approach. Barriers and facilitators to implementing SEEK will be probed quantitatively and qualitatively (see below). Among practices adopting SEEK, we will examine the association between practice characteristics and measures of completeness, speed, and quality of implementation from the SIC. We will examine relationships between practice characteristics and implementation by comparing the distribution of SIC scores in groups defined by practice characteristics. Finally, the most important predictors of degree of implementation will be determined using multivariable regression models with practice characteristics as predictors and SIC measures as outcomes. In addition to studying implementation at the practice level, we will analyze the relationship between PCP level measures of implementation (e.g., screening rates) and PCP characteristics, facilitators and barriers. These models will account for clustering of PCPs within practices, as described above.

**Aim 3. Examine the effectiveness of SEEK in reducing CM.** As in our previous studies, we will identify CM-related diagnoses, now via EHRs. We will review the EHR for each child (0-5) in each practice for two years prior to implementing SEEK and during implementation. The presence of CM-related ICD-10 codes will be recorded. The proportion of children with CM diagnoses before and during SEEK will be compared at each practice. Formal inference regarding the best estimate and statistical significance of pre-post differences will be based on a binary regression model with a random effect for site, similarly to Aim 1.

**Sample Size Considerations.** Our projected sample sizes (numbers of practices, professionals within each practice, and children in the practices) should provide good precision to estimate parameters and ample power to detect moderate associations. Table 4 below shows the detectable effect sizes for various comparisons, based on performing 2-sided .05-level tests and incorporate a 1.5-fold increase in variance and sample size to account for potential loss of power due to clustering of observations within practices and systems. In general, the detectable effect sizes are moderate, at plausible levels. We observed effect sizes of about 1.0 regarding Competence and Comfort in SEEK II. For Aim 2, assuming 90% of practices provide organizational information, we will estimate the rate of adoption of SEEK accurately,  $\pm$  15 percentage points.

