**Aim 2. Evaluate the impact of inner context variables (e.g., variation between pediatric and family medicine) on the SEEK implementation process and understand associated barriers and facilitators to successful service start-up and sustainment of SEEK delivery.** Using a mixed methods approach, standardized measures of the implementation process (Stages of Implementation Completion; SIC) and associated cost (Cost of Implementing New Strategies; COINS), will be integrated with qualitative interview data focusing on barriers and facilitators during implementation from exploration to sustainment. Variations in adoption, model fidelity, and sustainment, and the economic ramifications of each of the SEEK training and implementation strategies will be examined.

**Aim 3. Examine the effectiveness of the intervention strategies in preventing CM.** CM will be measured via prevalence of ICD-10 codes related to CM obtained from electronic health records for all children 0-5 attending the practices. **H1.** Incidence of CM will be reduced in practices after implementing SEEK. **H2.** Practices randomized to MOC training that successfully implement SEEK, will have lower incidences of CM than with the IND approach. We will also probe the influence of *SEEKonline* and the Traditional approach on CM rates. Additionally, implementation success, will be examined in relation to CM prevalence rates.

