nested within practices which are nested within the 5 healthcare systems. The participating systems will be randomized to one of two start times - 9 or 16 months from project start date, beginning with one pediatric and one family medicine system (cohort 1). Staggering the start time addresses the capacity limitations of the training and research staff.

**Sample.** We will offer SEEK to the 5 healthcare systems. Inclusionary criteria are: 1) practices not already implementing SEEK, 2) practices providing primary care to children, and 3) agreement to participate. The systems have indicated a general commitment to this project; they include 59 practices with 306 PCPs. Our recruitment efforts in SEEK II were very successful with 75% (18/24) of practices agreeing to participate, including all the PCPs in those practices. We plan to study 13 pediatric and 35 family medicine practices. If more practices are interested, we will select the first 48 choosing to participate. In the unlikely event that fewer than 48 are interested, we will approach other healthcare systems. In addition to 5 system leaders, we will recruit 5 groups of participants: 1) all 48 practice leaders, 2) 275 PCPs, 3) 16 behavioral health professionals, 4) 96 ancillary staff, and 5) 288 parents (6 per practice). These estimates are based on current staffing. Smaller subsamples will be purposively selected for qualitative interviews according to practice type, training strategy and presence of integrated behavioral health.

We will also request limited consent from practice leaders and PCPs who opt out to briefly probe their decision. We will ascertain aggregated ICD-10CM-related diagnoses on all children 0-5 attending the practices (N~90,000). Based on our experience, we anticipate 60% of practice leaders and PCPs will be female as will be most of the other participants. Different regions provide diversity in terms of urban, suburban and rural locations, and racial/ethnic diversity (e.g., 2 systems serve a predominantly Latino population). Three systems have integrated behavioral health professionals. These contextual factors will be considered in all analyses.

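### As worded, the Aim 3 pre-post test of child maltreatment diagnoses leaves practice-to-practice variation in change out of its standard error

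*Combined protocol and SAP*

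**What the plan says.** The Data Analysis Plan (General Considerations) gives one rule for clustering: "In these models, we will include a random effect for system and for practice", plus one effect per person where a person is measured repeatedly. It adds: "Below we highlight the main analyses for each Aim".

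Only the Aim 1 Competence model is written out. Its three random terms "are random effects for system, practice and PCP respectively". The outcome carries a time index; none of the random terms does.

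The Aim 3 model is described in a clause. Before-and-during proportions are to be set against each other by practice ("The proportion of children with CM diagnoses before and during SEEK will be compared at each practice"). The next sentence assigns the estimate and significance test of the pre-post difference to a "binary regression model with a random effect for site, similarly to Aim 1".

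The documents contain no practice-by-period effect, random slope, robust variance or practice-level formal test. The 1.5-fold variance allowance for clustering (Sample Size Considerations) enters the power table only.

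**The concern.** A time-constant practice effect is shared by a practice's before and during periods, so it drops out, almost entirely, when the two are subtracted. A system intercept does the same. What is left is the within-practice sampling variance, which for binomial data is fixed by the prevalence. If some practices' CM rates fall and others' rise, for whatever reason, the estimate becomes less certain but the model's standard error does not grow.

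At stake is Aim 3 H1, the claim that CM falls after SEEK is introduced. If change varies between practices, the test can declare a reduction too often at the two-sided 5% level, and the interval is too narrow. The plan itself treats variation in change as a possibility: under Specific Aims, Aim 3, "implementation success, will be examined in relation to CM prevalence rates".

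**Working it through.** **Inputs from the documents.** 48 practices (Sample); 98,000 in the N-per-group column of Table 4, Aim 3 row, taken here as the number per period; prevalences of 5% and 10% (Table 4) and 1% (its note 3, lower end); two-sided 0.05; 1.5-fold variance allowance.

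**Assumed, because not given.** The SD across practices of the true change in CM rate; an offset f of 0 to 0.35 for children contributing to both periods; equal practice sizes.

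**Step 1: the plan's own figures.** Table 4, Aim 1a: (1.960 + 0.842) × √(1.5 × 2/137) = 0.415, against the stated 0.42. This reproduces and shows how the 1.5 is used. In the Aim 3 row, factor 1.5 and 98,000 per group give 98.9% power for 5% vs 4.5% and 68.1% for 10% vs 9.6%. The second figure is short of 80%, but that is a separate matter and nothing below depends on it.

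**Step 2: true variance relative to model variance.** With m = 98,000/48 = 2,042 children per practice-period and prevalence p,

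factor = (1 − f) + m × SD² / [2p(1 − p)]

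type I error = 2 × [1 − Φ(1.96/√factor)]

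Worked case, p = 0.05 and SD = 0.005: 2,042 × 0.000025 / 0.095 = 0.537. The factor is 1.537 at f = 0 (1.96/1.240 = 1.58, error 11%) and 1.187 at f = 0.35 (1.96/1.090 = 1.80, error 7%).

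| Prevalence | SD of change (points) | Factor, f = 0.35 to 0 | Type I error |
|---|---|---|---|
| 5% | 0.25 | 0.78–1.13 | 3–7% |
| 5% | 0.5 | 1.19–1.54 | 7–11% |
| 5% | 1.0 | 2.80–3.15 | 24–27% |
| 10% | 0.25 | 0.72–1.07 | 2–6% |
| 10% | 0.5 | 0.93–1.28 | 4–8% |
| 10% | 1.0 | 1.78–2.13 | 14–18% |
| 1% | 0.1 | 0.75–1.10 | 2–6% |
| 1% | 0.2 | 1.06–1.41 | 6–10% |
| 1% | 0.4 | 2.30–2.65 | 20–23% |

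**Step 3: the plan's 1.5 read as applying to this contrast.** 1.96/√1.5 = 1.60, so the test runs at about 11%. At 5% prevalence this corresponds to SD = √(0.5 × 0.095/2,042) = 0.48 points, a practice-by-period intraclass correlation of only 0.5/2,042 = 0.00025.

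**Step 4: simulation of the model as worded.** A random-intercept logistic model was fitted to 400 null trials per setting (5% prevalence, no child in both periods). The SD of change was 0, 0.1, 0.2 and 0.3 on the logit scale; multiplied by 0.0475, these are about 0, 0.48, 0.95 and 1.43 points.

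| Logit SD | Mean model SE | Actual SD of estimate | Type I, model as worded | Type I, paired t on 48 changes |
|---|---|---|---|---|
| 0 | 0.0202 | 0.021 | 5.8% | 5.8% |
| 0.1 | 0.0202 | 0.026 | 12.8% | 4.8% |
| 0.2 | 0.0202 | 0.036 | 28.8% | 4.5% |
| 0.3 | 0.0201 | 0.050 | 45.0% | 4.0% |

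The model's standard error does not respond to variation in change. A practice-stratified Mantel-Haenszel test, used as a stand-in (10,000 replicates), gave 4.9%, 6.3%, 11.1% and 27.0% at SD 0, 0.25, 0.5 and 1.0 points; the paired t test stayed at 4.8–5.3%.

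**Step 5: Aim 1, PCPQ scales.** Assumptions: total variance 1, same-PCP correlation 0.5, practice variance 0.05, 48 practices of 5 or 6 PCPs. Type I error for POST × MOC is 2 × [1 − Φ(1.96 × model SE/true SE)].

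| Correlation of a practice's baseline and follow-up levels | Model SE/true SE | Type I error |
|---|---|---|
| 0.95 | 0.1078/0.1089 | 5.2% |
| 0.8 | 0.1080/0.1131 | 6.1% |
| 0.5 | 0.1088/0.1284 | 9.7% |
| 0.33 | 0.1096/0.1472 | 14.4% |

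**Step 6: Aim 1, EHR outcomes.** Screening and receipt of services have many visits per practice. A linear approximation with an assumed 100 visits per practice-period and intraclass correlation 0.05 gives model and true variances of 0.0175 and 0.0217 at correlation 0.95 (1.96 × √ratio = 1.76, error 8%), and 0.0174 and 0.0340 at 0.8 (1.40, error 16%).

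**The case against.** The best defence is that the Aim 3 model is not written out. The plan says it only highlights the main analyses, and it does mention a comparison at each practice. A practice-by-period term might be intended. That stands as a reason for caution about intent. But the by-practice comparison is descriptive, formal inference is assigned elsewhere, and the wording points back to Aim 1, whose random terms are time-constant.

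The second defence also stands: the size rests on assumptions. No intraclass correlation, practice-by-period variance or overlap of children is given, and the offset range of 0 to 0.35 has no source in the documents. The stated link between implementation success and CM rates is an analysis to be done, not evidence that change varies. Under the null, variation would have to come from elsewhere, such as local coding or case mix.

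Third, 98,000 per period may not be right. The Sample section gives about 90,000 children, and the windows differ (two years before; about 32 months during, months 9–41 and 16–48). At 90,000, m = 1,875 and the 5%, SD 0.5 case with f = 0 has factor 1.49 and error 10.9% instead of 11.4%. That does not alter the point.

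A reader might infer that the randomised MOC versus IND comparison of Competence is undermined to the same degree. The documents do not support this: they do not show that PCPQ change differs between practices, clusters are small, and the excess is slight at plausible pre/post correlations. Nor does that reassurance carry over to EHR screening and services (Step 6).

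**Conclusion.** The point holds for Aim 3 as worded and should be fixed. Practice variation in change does not enter the standard error of the pre-post test. How much this matters is unknown: no error if change does not vary, a conservative test if variation is slight and many children appear in both periods, and type I error of about 7–11% at SD 0.5 points or 24–27% at 1.0 point (5% prevalence, 98,000 per period, equal practices). It would be wrong to say that the plan's error rate is any one of these figures, or that the authors have ruled out a practice-by-period term.

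For PCPQ scales under Aim 1 this is a refinement: 5.2–6.1% at pre/post practice correlation 0.95–0.8, and larger only if that correlation is weak.

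**What to change.** **Aim 3.** Write the model out, and do one of the following:
- add a practice-by-period (practice × POST) random effect, with small-sample degrees of freedom based on the 48 practices; or
- base formal inference on the 48 paired practice-level changes.

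The paired version is feasible with the aggregate EHR data described under Measures, and it absorbs children seen in both periods. State whether changes are weighted by practice size: unweighted, it targets the practice-average change, not the child-weighted one.

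Because participants are "nested within practices which are nested within the 5 healthcare systems", report a sensitivity analysis for system-by-period shifts. If 5% or 10% of the variance of practice changes is shared within systems, the 48-practice test runs at 10% or 15%. A test on five system means holds 5% but has low power.

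**Aim 1 outcomes with a baseline.** Use the same practice × POST term.

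**Cost.** One RANDOM statement and a degrees-of-freedom option in the GLIMMIX procedure already named, and somewhat wider intervals. Power for 5% vs 4.5% follows from Φ(0.005/SE − 1.96), with SE² = factor × 0.090475/98,000: about 99% at factor 1.54 (SD 0.5 points) and 83% at 3.15 (SD 1.0). For Aim 1a PCPQ the corrected detectable effect is 0.31–0.32 at correlation 0.95–0.8 and 0.41 at 0.33, within the stated 0.42.

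**Limit.** This corrects the standard error only. It does not separate SEEK from a secular trend or coding change common to all practices, so a repaired test is not by itself sound evidence that SEEK reduced CM.

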**Training.** Two training strategies will be tested (see Table 1), both increasingly used with PCPs, and developed in accordance with principles of adult learning. First, *SEEK Maintenance of Certification (MOC-4)* is an example of a structured Quality Improvement (QI) project approved by the American Boards of Pediatrics and of Family Medicine, required of physicians to maintain Board certification. It includes viewing the training videos and implementing SEEK in one's practice and conducting the QI Plan-Do-Study-Act cycle. This PDSA cycle involves learning from data collected before and during SEEK's implementation to assess and improve the process. Four one-hour webinars over 4 months enable collaborative learning and mentoring. Second, Independent online (IND) training is a student-centered approach; it involves viewing the training videos over 2-3 hours and passing the post-test. Both approaches include three 1-hour consultations in the ensuing year and offer CME credits toward state licensure. Although both are convenient, we hypothesize that the interactive MOC-4 training will lead to more efficient and competent adoption of SEEK.

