**Table 1. SEEK Training Strategies**

SEEK MOC-4	Independent Online (IND)
Eligible for MOC 4 and CME credits	Eligible for MOC CME credits
Engage in SEEK QI project – PDSA cycle	N/A
Participate in four 1-hr. webinars	N/A
View SEEK training videos (2.5 hours)	View SEEK training videos
Pass SEEK Post-test	Pass SEEK Post-test
Participate in 3 one-hour consultation sessions	Participate in 3 one-hour consultation sessions

**Facilitation of Service Delivery.** SEEKonline is software to efficiently implement SEEK via a secure web-based system interfacing with a practice's EHR. SEEKonline has been developed and is currently being beta tested. Its effectiveness in improving implementation outcomes compared to the Traditional paper-and-pencil approach has yet to be examined. Data are stored in a Microsoft SQL Server Database, in an isolated, secure, private cloud environment, behind a fully HIPAA-certified network security device. SEEKonline enables parents to privately complete the SEEK PQ before a child's checkup. Responses are available to PCPs

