## Implementation framework: EPIS model.

The implementation approach is anchored in four stages of the EPIS conceptual model: Exploration, adoption/Preparation,

Implementation, and Sustainment. The strong evidence for SEEK's effectiveness has been underscored by its listing on the websites of the CDC, AHRQ, AAP, and by the California Clearinghouse for Evidence-Based Interventions in Child Welfare. Early adopters are increasingly implementing SEEK in primary care settings, including in Sweden. Four of the 5 healthcare systems in this proposal have implemented SEEK in some of their practices. However, practices within these systems operate independently of one another, and there should not be contamination among them. Each practice has its own lead physician, PCPs and administrative staff and several have integrated behavioral health. Given that early adopters are estimated to be 10% of those eligible and that medical innovations can take 17 years to be adopted, it is unlikely that SEEK's potential public health benefit will be realized without better methods for scaling up.

**Design.** The proposed implementation study is the first involving SEEK. We selected a rigorous Hybrid Type III design which is an approach to examine implementation outcomes while also examining SEEK's effectiveness in preventing CM, measured by EHR indicators. Type III designs are facilitated by good EHR systems due to the low cost of data routinely gathered for clinical, services, and financial purposes. This allows more resources to address the implementation outcomes of SEEK strategies in routine practice settings. In the past 4 years, over 80 papers reported use of hybrid designs. Practices will be randomized to one of the two training strategies (IND vs. MOC). Practices, however, will be able to select the facilitation strategy (SEEKonline or Traditional) as we are not able to require this of participants. The design accounts for heterogeneity in geography, size of healthcare systems, type of primary care (pediatric and family medicine), and presence of integrated behavioral health (see strong support letters from healthcare systems in Texas, Ohio, Utah, Wisconsin and North Carolina). As shown in Figure 2, professionals, office staff and parents are

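### The secondary comparison by training received gives up the practice randomisation and is open to bias toward MOC; a complier estimate would keep the randomisation

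*Combined protocol and SAP*

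**What the plan says.** Under Aim 1 of the Data Analysis Plan, intention to treat is the primary approach and the reason is given: "To avoid possible biases due to selective attrition from the training". The next sentence reads: "Secondary analyses will be based on groups defined by training received". Nothing further is said about that analysis. There is no definition of having received MOC or IND, no rule for partial completers, no adjustment set and no separate model.

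The Training paragraph and Table 1 (Section A) set out the two programmes. Of IND: "it involves viewing the training videos over 2-3 hours and passing the post-test". Of MOC: "It includes viewing the training videos and implementing SEEK in one's practice and conducting the QI Plan-Do-Study-Act cycle". Table 1 gives both arms the videos, the post-test and three consultations. Only the MOC column carries the QI project and the entry "Participate in four 1-hr. webinars"; both are marked not applicable for IND.

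The Design paragraph and the Procedures randomise practices. The example model for Competence codes training at the level of the individual: "MOC = 1 if the PCP was trained using MOC and 0 if IND". It contains no MOC main effect: "Note this model assumes that the mean baseline scores are the same in both groups, as recommended for randomized studies".

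**The concern.** Two features combine. First, once PCPs are grouped by what they took up rather than by what their practice was assigned, the groups differ by self-selection, which is the bias named one sentence earlier. Second, the programmes are nested. A MOC PCP who finishes the shared parts and takes up neither the webinars nor the QI project has had the IND content, while no route is described by which an IND PCP could obtain the MOC-only parts. Movement between groups can therefore run in one direction only.

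If those who leave the MOC-only parts are less engaged, and less engaged PCPs score lower on Competence or Comfort whatever their training, removing them from MOC raises the MOC mean. Adding them to IND would also lower the IND mean. Both push toward H1 of Aim 1, which predicts an advantage for MOC. At stake is the only analysis the plan names for training actually received: it could show a MOC advantage where there is none.

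**Working it through.** **The plan's own figure.** Table 4 gives 137 PCPs per group and a detectable effect of 0.42 SD (80% power, two-sided 0.05, variance inflated 1.5-fold). Check: √(2 × 1.5 / 137) × (1.960 + 0.842) = 0.148 × 2.802 = 0.415, or 0.417 with a t reference. Both round to 0.42, so the figure reproduces. It serves below only as a scale.

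**Assumed inputs.** The documents give none of these.
- The true MOC effect is zero and the arms are of equal size.
- A share *f* of PCPs in either arm would not complete the MOC-only parts.
- Those PCPs score *g* SD lower than the rest, whatever their training.

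**Formulae.** Set each randomised arm's mean to 0. MOC completers then average *fg* and MOC non-completers *fg* − *g*.
- Non-completers moved to IND: the enlarged IND group averages *f*(*fg* − *g*)/(1 + *f*), so the difference is 2*fg*/(1 + *f*).
- Non-completers excluded from MOC, or set aside as a third group: MOC completers are compared with the whole IND arm, so the difference is *fg*.
- Intention to treat: the difference is 0.

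**Results with *g* = 0.5 SD**

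| Drop-out *f* | Moved to IND | Excluded from MOC only |
|---|---|---|
| 20% | 0.20/1.2 = 0.167 SD | 0.10 SD |
| 30% | 0.30/1.3 = 0.231 SD | 0.15 SD |
| 40% | 0.40/1.4 = 0.286 SD | 0.20 SD |

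Over *f* = 10–40% and *g* = 0.25–0.75 SD, the reclassified version runs from 0.05 to 0.43 SD.

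**False-positive rate at *f* = 20%, *g* = 0.5, with the plan's 1.5 variance factor**
- Moved to IND: groups of about 110 and 164; standard error √(1.5 × (1/109.6 + 1/164.4)) = 0.151; 0.167/0.151 = 1.10; a two-sided 0.05 test rejects about 20% of the time.
- Excluded from MOC only: about 10%.

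**What shrinks it (same *f* and *g*)**
- Baseline adjustment, with a baseline-to-follow-up correlation of 0.5: 0.167 SD falls to 0.125 SD if low engagement already lowers baseline by 0.25 SD, and to 0.083 SD if by 0.5 SD. If it does not show at baseline, nothing is removed.
- Failure of the shared core: suppose the least engaged 10% fail the videos or post-test in both arms and are excluded. The bias is 0.5 × 0.2/1.0 = 0.10 SD if the remaining MOC non-completers are moved to IND, and 0.5 × 0.1/0.9 = 0.056 SD if they are excluded. If all 20% fail the core in both arms and are excluded, it is 0.

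**The alternative estimate.** With one-way non-adherence, the complier average causal effect is the intention-to-treat difference divided by the MOC completion proportion. For example, 0.30 SD with 70% completion gives 0.30/0.70 = 0.43 SD. The standard error scales likewise: 0.148/0.70 = 0.211.

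**The case against.** The strongest reply is that the plan never says MOC non-completers become IND. A reader might infer that drop-outs can only end up in the IND group. The text does not support that, because exclusion or a third group fits the sentence equally well. A PCP who also misses the videos or post-test fits neither definition, and one who attends two webinars has had more than IND. This stands, and it is why both versions are shown. It does not remove the problem: exclusion and a third group still compare selected MOC completers with an unselected IND arm.

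The size is assumed throughout, and selective non-completion within IND could offset part or all of it. That also stands. The link between engagement and score is not documented either, although the plan's own worry about selective attrition presupposes something like it. Some of any gap between the secondary and primary results could be a genuine dose effect.

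A reader might also infer that the main Aim 1 result is compromised. It is not: intention to treat is primary and covers everyone randomised.

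Finally, the complier estimate is not assumption-free. PCPs in one practice share workflow, so non-completers may gain from partial attendance or from colleagues' MOC activity. In either case, dividing by the completion proportion overstates the effect on completers. This is a fair limit, and it must be stated with the result.

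**Conclusion.** The point holds for the secondary analysis. Grouping by training received breaks the practice randomisation and reintroduces the bias that the plan cites in favour of intention to treat. Because the programmes are nested, the only crossover the described content allows is MOC to IND. If non-completers tend to score lower and are either counted as IND or excluded from MOC only, the bias favours MOC.

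With no true effect, 20–40% drop-out and a 0.5 SD gap, it is about 0.17–0.29 SD or 0.10–0.20 SD respectively. These are illustrations, not predictions. The bias is smaller, and can vanish, under the conditions shown in the working. The example model's equal-baseline assumption is justified by randomisation, so that justification does not carry over to self-selected groups. The change should be made, but the trial's main conclusion does not depend on it.

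**What to change.** Replace the sentence on secondary analyses along these lines:

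- Define MOC completion in advance, in terms of webinars attended and PDSA steps done, and record it for every PCP.
- Keep every PCP in the arm to which the practice was randomised.
- Make the secondary estimate a complier average causal effect, with the randomised arm as instrument, MOC completion as exposure and practice-clustered standard errors.
- State that it assumes no effect of partial MOC attendance or of colleagues' MOC activity on non-completers, and that it overstates the effect if this fails.
- If an as-received comparison is kept, label it non-randomised, do not count MOC non-completers as IND, and do not rest it on the equal-baseline assumption.

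The cost is a few sentences, one extra model and a completion record. It should not be presumed that the record already exists through certification credit. The Training paragraph describes that requirement for physicians, whereas the PCP definition in Section A also includes nurse practitioners and physician assistants. The statistical price is a wider interval (the standard error rises by 1/0.70 = 1.43-fold over intention to treat at 70% completion) and one untestable assumption.
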